### **10.1.2.2 Visit 3 (Week -1, Injection training)**

The injection training will occur during the screening period after the eligibility criteria have been checked and it is confirmed that the patient is likely to be included. Patients aged  $\geq 12$  years (or another designated person such as parent, etc) will be trained to self-inject/inject with placebo for alirocumab. Patients 8 to 11 years old will be assigned a parent or another designated person who will be trained during the injection training visit or an alternative arrangement. In all cases, alternative arrangements for this required injection training may be allowed as needed, regardless of age.

Prior to the injection, a local topical anesthetic may be utilized as per the Investigator's judgment. Investigators will have the option of providing a second placebo kit for patients/parents who require additional injection training prior to enrollment.

Patients can be enrolled after the injection training visit and as soon as eligibility is confirmed.

The injection training visit at Week -1 can take place at the same visit as D1 as per the site or patient preference.

The following additional procedures/assessments will be performed at the injection training visit:

- IRT contact.
- Check of stability of background LMT, including apheresis schedule (if applicable).
- Collect AEs.

### **10.1.3 Treatment period**

The overall treatment period is 48 weeks in duration.

All patients will receive subcutaneously (SC) either 75 or 150 mg alirocumab Q2W at entry, depending on their BW, without any dose adjustment up to Week 12. After Week 12, the dose of alirocumab can be adjusted in case of weight change after baseline, such that the dose corresponds to the patient's BW:

- 75 mg for BW <50 kg.
- 150 mg for BW  $\geq 50$  kg.

For patients treated with apheresis, the frequency will be fixed to the individual patient's established schedule up to Week 12. After Week 12, the frequency of apheresis can be adapted following Investigator judgment.

For dosing and timing of injection details, see [Section 8.1](#).

The first IMP injection from the study treatment kit allocated by IRT will be administered at the site on the day of entry and as close as possible after their entry into the study. Patients will be monitored at the investigational site for at least 30 minutes after this first injection. Subsequent injections will be performed at a patient-preferred location (eg, home). All of the IMP injections

can be performed by a trained patient (self-injection if aged  $\geq 12$  years), parent, or another designated person, or alternative arrangements for injection administration will be allowed as needed (eg, return to the investigational site). It is suggested that patients  $\geq 12$  years old, who are trained to self-inject, do so with parental (or another designated person) supervision; however, this is not mandatory. The Investigator may evaluate the sustained reliability of this practice on a case by case basis given the variable adolescent ages, maturity levels, availability of the caregiver, or other relevant considerations, with the patient. The final decision as to whether supervision is appropriate for self-injection of alirocumab for patients  $\geq 12$  years old is per Investigator discretion. Prior to any injection, a local topical anesthetic may be utilized as per the Investigator's recommendation.

The laboratory measurement of lipid parameters will be performed by a central laboratory. The results will be communicated to the sites.

Statin and other LMT, including apheresis, (if applicable) should be stable during the treatment period barring exceptional circumstances whereby overriding concerns (including but not limited to triglyceride alert posted by the central laboratory) warrant such changes, as per the Investigator's judgment.

#### **10.1.3.1 Visit 4 (Day 1, Week 0, Enrollment visit)**

The following procedures/assessments will be performed:

- Assessment of inclusion/exclusion criteria.
- Concomitant medication recording.
- Check of stability of background LMT, including apheresis (if applicable).
- Review of diet.
- Vital signs.
- Body weight.
- Body height.
- IRT contact.
- Inclusion in study.
- Collect AEs.
- Fasting blood sampling for:
  - Total-C, LDL-C, HDL-C, TG, and non-HDL-C (pre-apheresis and post-apheresis, if applicable).
  - Apo B, Apo A-1, ratio Apo B/Apo A-1, and Lp (a) (pre-apheresis, if applicable).
  - Hematology and chemistry.
  - CPK-MB and cardiac troponin.
  - CPK.
  - Liver panel.

- Anti-alirocumab antibodies (ADA) (pre-apheresis, if applicable).
- Serum alirocumab concentration (PK) and PCSK9 concentrations (pre-apheresis and post-apheresis, if applicable).
- Pregnancy test (urine).
- IMP administration; patients will remain under observation at the site for 30 minutes post-injection.
- IMP kit dispensation (including treatment administration package, patient diary, and injection instruction manual, as needed).

**Injection training:** Further injection training can be provided at the enrollment visit Week 0/Day 1 when the patient/parent or a trained designated person injects the first dose of IMP allocated by IRT. Additional training can be offered at scheduled or unscheduled visits within the scheduled treatment period, as per patient/parent or Investigator's judgment.

It is suggested that patients  $\geq 12$  years old, who are trained to self-inject, do so with parental (or another designated person) supervision; however, this is not mandatory. The Investigator may evaluate the sustained reliability of this practice on a case by case basis given the variable adolescent ages, maturity levels, availability of the caregiver, or other relevant considerations, with the patient. The final decision as to whether supervision is appropriate for self-injection of alirocumab for patients  $\geq 12$  years old is per Investigator discretion.

#### **10.1.3.2 Visit 5 (Week 4)**

The following procedures/assessments will be performed:

- Compliance check of IMP and data collection on IMP administration.
- Concomitant medication recording.
- Check of stability of background LMT, including apheresis (if applicable).
- Review of diet.
- Collect AEs.
- Vital signs.
- Body weight.
- Body height.
- Fasting blood sampling for:
  - Total-C, LDL-C, HDL-C, TG, and non-HDL-C (pre-apheresis and post-apheresis, if applicable).
  - Hematology and chemistry.
  - Liver panel.
- IMP administration.

### **10.1.3.3 Visit 6 (Week 12)**

The following procedures/assessments will be performed:

- Compliance check of IMP and data collection on IMP administration
- Concomitant medication recording.
- Check of stability of background LMT, including apheresis (if applicable).
- Review of diet.
- Collect AEs.
- Vital signs.
- Physical examination.
- Body weight.
- Body height.
- IRT contact.
- Tanner stage.
- Fasting blood sampling for:
  - Total-C, LDL-C, HDL-C, TG, and non-HDL-C (pre-apheresis and post-apheresis, if applicable).
  - Apo B, Apo A-1, ratio Apo B/Apo A-1, and Lp (a) (pre-apheresis, if applicable).
  - Hematology and chemistry.
  - HbA1c.
  - CPK-MB and cardiac troponin.
  - CPK.
  - Liver panel.
  - Anti-alirocumab antibodies (ADA) (pre-apheresis, if applicable).
  - Serum alirocumab concentration (PK) and PCSK9 concentrations (pre-apheresis and post-apheresis, if applicable).
- Pregnancy test (urine).
- IMP kit dispensation (including treatment administration package, patient diary, and injection instruction manual, as needed).
- IMP administration.

#### **10.1.3.4 Visit 7 (Week 24)**

The following procedures/assessments will be performed:

- Compliance check of IMP and data collection on IMP administration.
- Concomitant medication recording.
- Check of stability of background LMT, including apheresis (if applicable).
- Review of diet.
- Collect AEs.
- Vital signs.
- Physical examination.
- Body weight.
- Body height.
- Tanner stage.
- IRT contact.
- Fasting blood sampling for:
  - Total-C, LDL-C, HDL-C, TG, and non-HDL-C (pre-apheresis and post-apheresis, if applicable).
  - Apo B, Apo A-1, ratio Apo B/Apo A-1, and Lp (a) (pre-apheresis, if applicable).
  - Hematology and chemistry.
  - HbA1c.
  - CPK.
  - Liver panel.
  - Anti-alirocumab antibodies (ADA) (pre-apheresis, if applicable).
  - Serum alirocumab concentration (PK) and PCSK9 concentrations (pre-apheresis and post-apheresis, if applicable).
- Pregnancy test (urine).
- IMP kit dispensation (including treatment administration package, patient diary, and injection instruction manual, as needed).
- IMP administration.

#### **10.1.3.5 Visit 8 (Week 36)**

The following procedures/assessments will be performed:

- Compliance check of IMP and data collection on IMP administration.
- Concomitant medication recording.
- Check of stability of background LMT, including apheresis (if applicable).
- Review of diet.
- Collect AEs.
- Vital signs.
- Body weight.
- IRT contact.
- Pregnancy test (urine).
- IMP kit dispensation (including treatment administration package, patient diary, and injection instruction manual, as needed).
- IMP administration.

#### **10.1.3.6 Visit 9 (Week 48, end of the treatment period visit)**

The following procedures/assessments will be performed:

- Compliance check of IMP and data collection on IMP administration.
- Concomitant medication recording.
- Check of stability of background LMT.
- Review of diet.
- Collect AEs.
- Vital signs.
- Physical examination.
- Body weight.
- Body height.
- Tanner stage.
- IRT contact.
- Fasting blood sampling for:
  - Total-C, LDL-C, HDL-C, TG, and non-HDL-C (pre-apheresis and post-apheresis, if applicable).
  - Apo B, Apo A-1, ratio Apo B/Apo A-1, and Lp (a) (pre-apheresis, if applicable).

- Hematology and chemistry.
- HbA1c.
- CPK.
- Liver panel.
- Anti-alirocumab antibodies (ADA) (pre-apheresis, if applicable).
- Serum alirocumab concentration (PK) and PCSK9 concentrations (pre-apheresis and post-apheresis, if applicable).
- Pregnancy test (urine).

#### **10.1.4 Follow-up**

A follow-up call will be planned 10 weeks after the last IMP injection, ie. 8 weeks after the EOT visit, for the patients who complete the study and for the patients who discontinue early for any reason.

The following procedures/assessments will be performed remotely:

- Concomitant medication recording.
- Collect AEs.
- IRT contact.

#### **10.2 DEFINITION OF SOURCE DATA**

Evaluations that are reported in the eCRF must be supported by appropriately signed identified source documentation related but not limited to the following:

- Agreement, date, and signature of informed consent mentioning the study identification.
- Patient identification, last participation in a clinical trial, medical history, associated diseases, and data related to the studied pathology.
- Genotyping result, if available.
- Contraception methods for females of childbearing potential who are sexually active.
- Previous and concomitant medication (including LMT).
- Study identification.
- Treatment number and dates of administration.
- Dates of visits and assessments including the examination report.
- Vital signs, height, BW, and Tanner stage.
- Faxed central laboratory reports (dated and signed by the Investigator or Subinvestigator)

- IRT confirmation fax (screening, screen failure, discontinuation, EOT period, end of follow-up period, and end of study).
- Adverse events and follow-up:
  - In case of SAE, the site should file in the source document at least copies of the hospitalization reports and any relevant examination reports documenting the follow-up of the SAE.
- Date of premature study discontinuation (if any) and reason.

Source documentation may be found in the following:

- Patient's identity.
- Medical history.
- Hospital records.
- Nursing notes.
- Physician's notes.

### **10.3 HANDLING OF PATIENT TEMPORARY OR PERMANENT TREATMENT DISCONTINUATION AND OF PATIENT STUDY DISCONTINUATION**

The IMP should be continued whenever possible. In case the IMP is stopped, it should be determined whether the stop can be made temporarily; permanent IMP discontinuation should be a last resort. Any IMP discontinuation must be fully documented in the eCRF. In any case, the patient should remain in the study as long as possible.

Pregnancy will lead to definitive treatment discontinuation in all cases.

#### **10.3.1 Temporary treatment discontinuation with investigational medicinal product(s)**

Temporary treatment discontinuation (also referred to as treatment interruption) may be considered by the Investigator because of suspected AEs. Reinitiation of treatment with the IMP will be done under close and appropriate clinical/and or laboratory monitoring once the Investigator will have considered according to his/her best medical judgment that the responsibility of the IMP(s) in the occurrence of the concerned event was unlikely and if the selection criteria for the study are still met (refer to [Section 7.1](#) and [Section 7.2](#)).

For all temporary treatment discontinuations, duration must be recorded by the Investigator in the appropriate pages of the eCRF.

Treatment interruption is defined as one or more scheduled injections that are not administered to the patient as decided by the Investigator.

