## 7 SELECTION OF PATIENTS

### 7.1 INCLUSION CRITERIA

- I 01. Male and female children and adolescents aged 8 to 17 years genetically diagnosed with homozygous familial hypercholesterolemia inadequately controlled (see threshold mentioned in exclusion criterion E 02) despite treatment with optimal dose of statin with or without other LMTs, or non-statin LMTs if statin-intolerant, at stable dose(s) for at least 4 weeks.
- I 02. A signed informed consent indicating parental permission with or without patient assent, depending on capacity for understanding based on developmental maturity. In cases involving emancipated or mature minors with adequate decision-making capacity, or when otherwise permitted by law, a signed informed consent directly from patients.
- I 03. For patients on apheresis, currently undergoing stable LDL apheresis therapy for at least 4 weeks prior to the screening visit (Week -2) and have initiated apheresis treatment for at least 6 months (see Appendix A).

---

 Diagnosis of hoFH must be made either by previous genotyping (true homozygotes, compound heterozygotes, or double heterozygotes) or current genotyping performed after having been suspected by clinical criteria according to EAS Consensus Panel recommendations for diagnosis of HoFH. Previous genotyping refers to documented results that are available from prior genotyping testing supporting a diagnosis of hoFH. Current centralized genotyping refers to patients electing to undergo genotyping during the run-in period with results supporting a diagnosis of hoFH (see Appendix B).

 The optimal dose of statin is defined as the stable daily dose prescribed based on local guidelines or practice, or is the dose that is maximally tolerated due to adverse effects of higher doses. For patients not receiving the maximally tolerated dose of statin, statin intensification should be carefully considered prior to inclusion in this study in order to ensure that the addition of a non-statin LDL-C lowering therapy (ie, alirocumab) would be the next appropriate step in the management of the patient's hypercholesterolemia. The highest dose of statin should not exceed the maximum labeled dose of statin for pediatric patients as per the local prescribing information.

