### 7.2.1 Exclusion criteria related to study methodology

E 01. Children and adolescents aged less than 8 years or more than 17 years at the time of informed consent signature, unless different local regulation applies (eg, for Russia only: patients aged less than 12 years or more than 17 years at the time of informed consent signature).

*Note: Patients aged 8 to less than 10 years who have not had previous attempts to lower LDL-C by other means will be excluded.*

E 02. Patients with LDL-C (pre-apheresis, if applicable) less than 130 mg/dL (3.37 mmol/L) obtained during the screening period after the patient has been on stable apheresis procedure or LMT (ie, stable optimal dose of statin ± other stable LMTs, or stable non-statin LMTs in statin-intolerant patients) treatment for at least 4 weeks.

E 03. Patients with null LDLR mutations in both alleles.

E 04. Patients with BW less than 25 kg.

E 05. Patients aged 8 to 9 years not at Tanner Stage 1 and patients aged of 10 to 17 years not at least at Tanner Stage 2 in their development (See [Appendix C](#)).

E 06. Daily dose of statin that is above the maximum recommended dose for pediatric patients as per the local prescribing label.

E 07. Patients who will receive statin de novo during the run-in period.

E 08. Use of nutraceutical products or over-the-counter therapies that may affect lipids which have not been at a stable dose for at least 4 weeks prior to the screening visit.

E 09. Patients not previously instructed on a cholesterol-lowering diet prior to the screening visit.

E 10. Mipomersen in the last 5 months.

E 11. Patients with uncontrolled (ie, hemoglobin A1c [HbA1c] >9% at the screening visit) Type 1 or 2 diabetes mellitus.

E 12. Patients with known uncontrolled thyroid disease (ie, thyroid-stimulating hormone levels outside of the laboratory's reference range within the past 6 months, or with elevated free T3 or T4 and with clinical symptoms of hyperthyroidism).

E 13. Patients who use systemic corticosteroids.

*Note: Topical, intra-articular, nasal, inhaled, and ophthalmic steroid therapies are not considered as 'systemic' and are allowed.*

E 14. Patients with uncontrolled (ie, systolic blood pressure [SBP] or diastolic blood pressure [DBP] above local guidelines or equivalent) hypertension.

E 15. Fasting triglycerides >350 mg/dL (3.95 mmol/L) at the screening visit.

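### Section 10.3.1 makes restart after a hold for a suspected AE depend on all selection criteria, so E 05 (Tanner stage by age) can keep a child off alirocumab for normal development

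*Protocol*

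**What the plan says.** Section 10.3 sets the aim that "permanent IMP discontinuation should be a last resort". Under Section 10.3.1 a temporary stop "may be considered by the Investigator because of suspected AEs". For a suspected drug-related allergic event, Section 10.6.2 makes the interruption mandatory and refers back to 10.3.1.

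Restart takes place under close clinical and/or laboratory monitoring. It has two conditions: the investigator considers the IMP's responsibility for the "concerned event was unlikely and if the selection criteria for the study are still met". The reference is to Sections 7.1 and 7.2 without selection.

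The criteria most exposed to the passage of time are:

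- **E 05** excludes children aged 8 to 9 who are not at Tanner Stage 1, and "patients aged of 10 to 17 years not at least at Tanner Stage 2 in their development". It has no time anchor.
- **I 01, age**: "Male and female children and adolescents aged 8 to 17 years genetically diagnosed with homozygous familial hypercholesterolemia". It has no anchor of its own, but E 01 excludes those "aged less than 8 years or more than 17 years at the time of informed consent signature".
- **I 01, control**: "inadequately controlled (see threshold mentioned in exclusion criterion E 02) despite treatment with optimal dose of statin". The threshold comes from E 02: "Patients with LDL-C (pre-apheresis, if applicable) less than 130 mg/dL (3.37 mmol/L) obtained during the screening period".

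**The concern.** Selection criteria decide who enters. Section 10.3.1 uses them again, months later, to decide who may resume treatment, and does not say which were meant for entry only. For safety items such as hypersensitivity or pregnancy, a second check is sensible. For criteria that describe a child's stage of development, it is not: the child changes for reasons unrelated to the event or the drug.

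At stake is continued therapy for a child with hoFH whose adverse event has been judged unlikely to be due to alirocumab. Sites would also have to decide for themselves whether to follow the sentence literally, so practice could differ between them.

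**Working it through.** The protocol states no figure on this point, so the check is mainly one of wording. A rough count follows.

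**Criterion by criterion, at a restart during the 48 weeks**

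| Criterion | Time anchor | Effect of re-applying it |
|---|---|---|
| E 05 | None | Child aged 10 at Stage 1, or aged 8 to 9 at Stage 2, is excluded |
| I 01 age | None in I 01; E 01 says consent | Child who turns 18 is excluded only if I 01 is read apart from E 01 |
| I 01 control | None in I 01; E 02 says screening period | Child below 130 mg/dL on drug is excluded only if I 01 is read apart from E 02 |

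E 05 admits only two states: aged 8 to 9 at Stage 1, or aged 10 or over at Stage 2 or above. A child passing from the first to the second must go through an excluded state, unless Stage 2 and the tenth birthday coincide. The bar lifts once the other change occurs, but that may be after the treatment period ends. Tanner stage is recorded at Weeks 12, 24 and 48, so sites will hold the evidence.

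**How many children**

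From the protocol: about 18 enrolled and at least 15 evaluable (11.1); ages 8 to 17, a span of 10 years; 48 weeks of treatment. Assumed, because the protocol gives nothing: entry age uniform over 8 to under 18, holds uniform over the 48 weeks, and 10% to 30% of children held for an AE.

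1. Turning 10 on study: (48/52)/10 = 9.2%, or 18 × 0.0923 = 1.7 children. Turning 18 on study: the same.
2. Birthday before the hold (mean hold time 24 weeks): (24/52)/10 = 4.6% per route.
3. Two birthday routes together, counting every child who turns 10 as still at Stage 1: 18 × 0.0923 × 0.10 = 0.17, and × 0.30 = 0.50. With 15 children: 0.14 to 0.42.
4. Step 3 omits Stage 2 before age 10, for which the protocol gives no timing. A ceiling for E 05 as a whole follows from who can meet it: only children aged 8 or 9 at entry, since older entrants must already be at Stage 2 (assuming stages do not reverse). That is 2/10 × 18 = 3.6 children. If every hold among them led to a bar: 3.6 × 0.10 = 0.36, and 3.6 × 0.30 = 1.08.
5. The E 05 ceiling passes one child only when the hold rate exceeds 1/3.6 = 28% and every such hold is barred. Adding the age-18 route on its weaker reading (18 × 0.0462 × 0.10 = 0.08; × 0.30 = 0.25) gives ceilings of 0.44 and 1.33.

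**LDL-C route, if I 01 control were re-applied**

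The fall needed to go below 130 mg/dL is 1 − 130/300 = 57% from 300 mg/dL (the treated level in Appendix B), 1 − 130/500 = 74% from 500 and 1 − 130/1000 = 87% from 1000. Section 4 describes hoFH as 500 to 1000 mg/dL and cites a mean fall of 24% in LDLR-defective patients on another PCSK9 inhibitor. A 24% fall reaches 130 only from 130/0.76 = 171 mg/dL or less, so the route matters only for children who enter near the threshold.

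**The case against.** The best defence is that selection criteria are entry criteria by nature. The flow chart assesses them only up to Day 1, E 01 dates age to consent, and E 02 dates LDL-C to the screening period. Read together, Sections 7.1 and 7.2 are not changed by a birthday or a good response. That largely stands for I 01. What remains there is that I 01 has no anchor of its own, that 10.3.1 calls on both sections, and that the word *still* invites a check of current status. The defence does not reach E 05, which nothing elsewhere dates.

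It is also fair to say that few children are involved and that the primary endpoint uses LDL-C values regardless of adherence (9.1.1). Both stand.

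A reader might infer a second gap: E 11 and E 16 to E 18 (HbA1c, eGFR, ALT/AST, CPK) are worded as screening-visit values, so restart would go without a laboratory check. Scheduled safety laboratories are indeed 24 weeks apart between Weeks 24 and 48. The wording of those criteria is as described, but the inference is not supported. A hold for an AE is an unscheduled event. Section 10.3.1 requires monitoring and a causality judgment. Section 10 and 10.3.3 call for abnormal values to be rechecked, and 10.3.3 stops the drug when continuing would be detrimental. Section 10.6.2.1 orders unscheduled laboratories for allergic events with skin involvement. ALT, CPK and renal abnormalities follow the Appendix F charts (10.4.6), which are not shown, so any remaining gap in thresholds cannot be judged.

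**Conclusion.** The point holds for E 05 as a matter of plain wording: followed as written, 10.3.1 keeps a child off treatment because of normal growth, after an event judged unlikely to be due to the drug. Where that bar outlasts the treatment period, it conflicts with the aim of Section 10.3. The I 01 items are secondary examples that depend on how a site reads the sections together.

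The size is small: probably under one child of 18. This rests on assumed uniform ages and hold times and an assumed hold rate of 10% to 30%. It is not a strict bound, because the timing of Stage 2 before age 10 is unknown.

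A reader might infer damage to the primary result. The documents do not support that, since the ITT estimand keeps the child's values. A barred child's later values would leave the on-treatment analyses once 21 days have passed since the last injection (11.4.2.2). One child is 1/18 = 5.6% to 1/15 = 6.7% of the data. The main cost falls on the child.

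**What to change.** Add one sentence to Section 10.3.1: *The age, LDL-C threshold and Tanner stage criteria (I 01 age and control, E 01, E 02, E 05) apply at entry only and are not re-applied at restart.*

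Leave current laboratory values at restart to the monitoring in 10.3.1, to 10.3.3 and to the Appendix F charts. Do not write E 16 to E 18 in as numeric bars. E 17, at more than 2 × ULN, is stricter than the ALT event of special interest in 10.4.1.3 (more than 3 × ULN when baseline is below ULN), so it could bar a child who meets no numeric stopping rule in 10.3.3. E 16 needs a current eGFR, which Section 10 calculates only at screening.

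The cost is one sentence in an amendment, with no added visits, samples or analyses. The same amendment can correct a clerical slip: Section 10.6.2 points to 10.3.2 for the permanent-stop criteria, but the list is in 10.3.3.
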